3.2.3 Sensitivity analyses

3.2.4 Supplementary analyses for primary endpoint in Part A

To assess the treatment effect when the participants adhere to the study treatment as directed, the difference (SAR443820 vs placebo) in the mean change from baseline in the ALSFRS-R total score to Week 24 will be analyzed in the ITT population based on data collected during the treatment-emergent period for the Part A using the same model as primary analysis. ALSFRS-R total scores obtained after the IMP discontinuation will be considered as missing.

3.2.5 Subgroup analyses for primary endpoint in Part A

To assess the homogeneity of the treatment effect across various subgroups, analyses will be performed on the primary endpoint across the following subgroups (categories with fewer than

10% participants will be combined with other categories; for factors with only two categories, no subgroup analysis will be performed if fewer than 10% participants in one category):

- Geographic region (US, non-US)
- Region (Europe, North America, Asia)
- Age at screening (≤ 40 , > 40 years)
- Sex (Male or Female)
- Race (White, Black or African American, Asian, Other)
- ALS onset region (bulbar or other areas)
- Use of riluzole (yes or no)
- Use of edaravone (yes or no)
- Use of the combination of sodium phenylbutyrate and taurursodiol (yes or no)

The estimated treatment effect (SAR443820 versus placebo) for the primary endpoint will be provided, as well as the corresponding 95% CI, for each subgroup separately, using the same method as applied in the primary analysis. Forest plots of differences in treatment group means and corresponding 95% CIs comparing SAR443820 to placebo within each subgroup will be provided.

Treatment by subgroup interaction and its p-value will be derived from a MMRM with terms for treatment, visit, randomization strata of the geographic region of the study site, ALS onset region (bulbar or other areas), use of riluzole (yes or no), use of edaravone (yes or no), use of the combination of sodium phenylbutyrate and taurursodiol (yes or no), treatment-by-visit interaction, disease duration (from first symptom onset to the screening visit), baseline ALSFRS-R score, baseline NfL, disease duration-by-visit interaction, baseline ALSFRS-R score-by-visit interaction, baseline NfL-by-visit interaction, subgroup (if different than the aforementioned covariates), subgroup-by-treatment interaction as covariates. If a quantitative treatment by subgroup interaction is detected with nominal p-value <0.1 for any subgroup factor, a further investigation will be performed to evaluate possible qualitative interaction.

3.3 SECONDARY ENDPOINT(S) ANALYSIS

The secondary endpoints detailed in this section are as follows:

Part A

- CAFS at Week 24
- change from baseline in SVC to Week 24
- change from baseline in muscle strength to Week 24
 - change from baseline in megascore to Week 24
 - change from baseline in grip strength to Week 24

- change from baseline in ALSAQ-5 to Week 24
- change from baseline in serum NfL to Week 24

Part B

- CAFS at Week 76 and Week 104
- change from baseline in the ALSFRS-R total score to Week 52, Week 76, and Week 104
- time from baseline to occurrence of either death or permanent assisted ventilation (>22 hours daily for >7 consecutive days), whichever comes first
- time from baseline to the occurrence of death
- change from baseline in SVC to Week 52, Week 76, and Week 104
- change from baseline in ALSAQ-5 to Week 52, Week 76, and Week 104
- change from baseline in serum NfL to Week 52

Other secondary endpoints analyses are defined in [Section 3.6.2](#) (AE, SAE), [Section 3.6.3.1](#) (laboratory abnormalities), [Section 3.7.1.1](#) (PK) and [Section 3.7.1.2](#) (PD).

3.3.1 Secondary endpoint(s)

3.3.1.1 Definition of endpoint(s)

SVC

SVC is measured in participants while they are in an upright position at least 3 trials per assessment or up to 5 trials when the highest and second highest of the first 3 measurements differ by 10% or more. SVC volumes are standardized to the percentage of the predicted normal value based on age, sex, and height [\(7\)](#). The highest SVC score among all attempts will be used for analysis.

Muscle Strength

The muscles measured in the study include upper-limb and lower-limb muscle groups. Bilateral hand grip will be measured using a grip dynamometer and all other muscles included in this study will be measured using a handheld dynamometer (HHD). For each muscle to be tested, 2 trials will be performed. If the variability of the 2 trials is 15% or less, values from both trials will be recorded and the higher score will be used for analysis. If the variability is greater than 15%, a 3rd trial will be performed, all the values will be recorded and the maximum value of the 3 trials will be accepted. The order of testing is standardized and should be the same for each session. Grip strength will be tested first, followed by the arms and then the legs.

HHD data will be analyzed by combined muscle groups named (megascores). To create a megascore, individual muscles will be standardized using table e-1 in [\(8\)](#), from which individual muscle means and SDs were calculated from 228 healthy people. Note that in [\(8\)](#), each muscle

strength was measured in lbs, so the corresponding mean and SD in table e-1 are transformed to kg by multiplying a constant 0.453592. Two decimal places are kept as in (8). The transformed table is provided below. Z scores for each muscle measurement will be calculated from these means and SDs by subtracting the corresponding mean and dividing by the corresponding SD. Individual Z scores will then be averaged to produce a total megascore including all available muscle groups. To handle the missing data, the derivation rule for primary analysis is determined as follows: If a participant has a missing value for one muscle measurement and continues to have the missing value through the final assessment (eg, at least 2 consecutive missing values up to the final assessment), then these missing values for this muscle measurement will be imputed as zero; all the other missing values will not be imputed.

Mean strength, standard deviation for all muscles in 228 normal volunteers (table e-1 in (8))

HHD	Mean (kg)	SD	HHD	Mean (kg)	SD
L shoulder flexion	13.48	4.20	R shoulder flexion	14.01	4.11
L elbow flexion	15.78	5.22	R elbow flexion	15.87	5.34
L elbow extension	12.80	3.96	R elbow extension	12.79	3.78
L wrist extension	11.35	3.96	R wrist extension	12.02	3.97
L hip flexion	19.90	7.19	R hip flexion	20.15	7.08
L knee flexion	16.65	5.96	R knee flexion	16.77	5.71
L knee extension	16.00	6.03	R knee extension	16.24	6.42
L ankle dorsiflexion	17.25	6.91	R ankle dorsiflexion	17.45	7.03
L first dorsal interosseous	5.07	1.74	R first dorsal interosseous	5.35	1.97

Each mean and SD are derived from the table e-1 in (8) by multiplying a constant 0.453592 to change the unit from lbs to kg.

Grip strength data will be analyzed by the scores collected from left hand and right hand respectively. To handle the missing data, the derivation rule for primary analysis is determined as follows: If a participant has a missing value at one visit and continues to have the missing value through the final assessment (eg, at least 2 consecutive missing values up to the final assessment), then these missing values will be imputed as zero; all the other missing values will not be imputed.

ALSAQ-5

The ALSAQ-5 consists of 5 items derived from the ALSAQ-40. The 5 items closely resemble those of the 5-dimension scores of the ALSAQ-40: eating and drinking; communication; activities of daily living/independence; physical mobility; and emotional functioning. The ALSAQ-5 has a recall period of the past 2 weeks and takes approximately 5 minutes to complete. Each item is scored on a 5-point Likert scale ranging from 0 (never) to 4 (always or cannot do at all) according to the frequency of a particular problem. Total scores range from 0 to 20, with higher scores indicative of greater physical and emotional limitations.

Serum NfL

Serum blood samples will be used to measure changes in NfL, a marker of neuronal injury. Levels of NfL in both cerebrospinal fluid and plasma have been reported to be increased and stable over time in participant with ALS compared to healthy controls. Patients with ALS with a fast progression rate have demonstrated higher levels of NfL in CSF and plasma than those with a slow progression rate. Only serum NfL will be measured in this study to reduce the collection burden on participants.

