	Change from baseline in slow vital capacity (SVC) (muscle strength, Amyotrophic Lateral Sclerosis Assessment Questionnaire (ALSAQ-5), serum neurofilament light chain (NfL)) to Week 24	ITT	Permanent study intervention discontinuation before Week 24 – regardless of treatment discontinuation (treatment policy)		These secondary endpoints will be analyzed using MMRM with change from baseline value up to Week 24 as response variable, and treatment, visit, randomization strata of the geographic region of the study site, ALS onset region (bulbar or other areas), use of riluzole (yes or no), use of edaravone (yes or no), use of the combination of sodium phenylbutyrate and taurursodiol (yes or no), treatment-by-visit interaction, disease duration (from first symptom onset to the screening visit), baseline value of the endpoint, baseline NfL (if different from the baseline value of the endpoint), disease duration-by-visit interaction, baseline value of the endpoint-by-visit interaction and

Endpoint Category (estimand)	Endpoint	Population	Intercurrent event(s) handling strategy	Estimands	Population-level summary (Analysis and missing data handling)
				baseline NfL-by-visit interaction (if different from the baseline value of the endpoint-by-visit interaction) as covariates. All available data will be used, and missing data will be handled by MMRM based on missing at random assumption. For muscle strength data, if there is a missing value for one muscle measurement which continues to have the missing value through the final assessment (eg, at least 2 consecutive missing values up to the final assessment), then these missing values for this muscle measurement will be imputed as zero; all the other missing values will not be imputed.	

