3.5 MULTIPLICITY ISSUES

To control the Type 1 error rate for the study, a hierarchical testing procedure will be applied at a 2-sided 5% significance level for primary and selected secondary endpoints in Part A, ie, each hypothesis will be formally tested only if the preceding one is significant at the 5% level. If

SAR443820 is significant for the primary endpoint in part A, a selective set of secondary endpoints in Part A will be tested following the hierarchical testing procedure shown below:

- CAFS score at Week 24
- Change from baseline in ALSAQ-5 to Week 24
- Change from baseline in serum NfL to Week 24
- Change from baseline in SVC to Week 24
- Change from baseline in megascore to Week 24

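### The megascore change can subtract means taken over different sets of muscles: if a weak muscle is first missing at Week 24, the decline is understated and can become an apparent gain

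*SAP*

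**What the plan says.** SAP 3.3.1.1 (Muscle Strength) converts each handheld-dynamometry value to a Z score "by subtracting the corresponding mean and dividing by the corresponding SD". The reference values are tabulated there for 18 muscles, nine per side ("Mean strength, standard deviation for all muscles in 228 normal volunteers"). The scores are then combined: "Individual Z scores will then be averaged to produce a total megascore including all available muscle groups".

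Missing values are handled muscle by muscle. Zero is imputed when a participant "continues to have the missing value through the final assessment (eg, at least 2 consecutive missing values up to the final assessment"). For anything else, "all the other missing values will not be imputed". The estimand table in SAP 1.2.1 (Table 2) repeats the rule: "if there is a missing value for one muscle measurement which continues to have the missing value through the final assessment".

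The visible text gives no fixed denominator, no minimum number of muscles, and no requirement that the baseline and visit means use the same muscles.

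The endpoint is confirmatory. In SAP 3.5 "a hierarchical testing procedure will be applied at a 2-sided 5% significance level", and the last entry in the Part A list is "Change from baseline in megascore to Week 24".

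**The concern.** A change from baseline should compare like with like. Here each visit's megascore is a mean over the muscles that happen to have a value, so the change can be a mean over 14 or 16 muscles minus a mean over 18. When a muscle leaves the average, the mean of the rest moves even if no remaining muscle has changed. It moves up if the departing muscle was weaker than the others and down if it was stronger.

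The zero rule covers a muscle already missing at the previous assessment. It does not clearly cover one first missing at Week 24, which has a single missing value and no consecutive pair. Week 24 is the visit that is tested. Loss of one muscle can therefore be scored as zero if it happens one visit earlier and disappear from the score if it happens at Week 24.

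The repeated-measures model cannot correct this. Its missing-at-random assumption deals with megascores that are absent. Here the megascore is present and is treated as observed. The rank ANCOVA in SAP 3.3.1.2 analyses the same derived value.

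**Working it through.** The plan states no figure for this rule, so there is none to reproduce. The check uses the SAP's table plus assumed strengths.

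**From the SAP table.** Z at 0 kg = −mean/SD:
- L first dorsal interosseous: −5.07/1.74 = −2.914
- R first dorsal interosseous: −5.35/1.97 = −2.716
- L wrist extension: −11.35/3.96 = −2.866
- R wrist extension: −12.02/3.97 = −3.028

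Over all 18 muscles the range is −3.41 to −2.48, mean −2.90.

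**Assumed (not in the documents).** The lost muscles start 0.25, 0.5 or 1.0 SD above 0 kg and are missing only at Week 24. All other muscles start at Z = −1.0 and fall by 0.1, 0.2 or 0.3. Either the two interossei are lost, or those plus the two wrist extensors.

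**Formulas**, with k of 18 muscles lost:
- As written: mean Z of the remaining 18 − k at Week 24, minus mean Z of all 18 at baseline.
- Paired: mean of (Z at Week 24 − Z at baseline) over the remaining 18 − k.
- Scored 0 kg: mean of all 18 at Week 24 with the lost muscles at 0 kg, minus the baseline mean.
- As written minus paired = (k/18) × (baseline mean Z of the others − baseline mean Z of the lost muscles). This does not depend on how far the others fall.

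**Example, two muscles, 0.5 SD, others falling 0.1.** The lost muscles start at −2.414 and −2.216, sum −4.630. Baseline = (−4.630 − 16)/18 = −1.146. As written: −1.100 + 1.146 = **+0.046**. Paired: **−0.100**. Scored 0 kg: (−5.630 − 17.6)/18 + 1.146 = **−0.144**.

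**Example, four muscles, same settings.** Baseline = (−9.523 − 14)/18 = −1.307. As written: **+0.207**. Paired: **−0.100**. Scored 0 kg: (−11.523 − 15.4)/18 + 1.307 = **−0.189**.

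**All 18 scenarios:**

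| Muscles lost | Start above 0 kg | Excess over paired | As written when others fall 0.1 / 0.2 / 0.3 |
|---|---|---|---|
| 2 | 0.25 SD | 0.174 | +0.074 / −0.026 / −0.126 |
| 2 | 0.5 SD | 0.146 | +0.046 / −0.054 / −0.154 |
| 2 | 1.0 SD | 0.091 | −0.009 / −0.109 / −0.209 |
| 4 | 0.25 SD | 0.362 | +0.262 / +0.162 / +0.062 |
| 4 | 0.5 SD | 0.307 | +0.207 / +0.107 / +0.007 |
| 4 | 1.0 SD | 0.196 | +0.096 / −0.004 / −0.104 |

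The excess is 0.09 to 0.36 Z. A decline appears as a gain in 2 of 9 scenarios with two muscles lost and in 7 of 9 with four. The excess is also the break-even point: once the others fall by more than that, the score shows a decline, but too small a one.

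**Second parameterisation.** Put 17 muscles at 60% of the healthy mean, unchanged, and the L interosseous at 10% before it is lost. The change is (−1.161 + 2.622)/18 = +0.081 as written, against −0.1 × 2.914/18 = −0.016 at 0 kg. If the lost muscle was also at 60%, the change as written is about 0.000. There is then no gain, but the loss is not counted (−0.6 × 2.914/18 = −0.097 at 0 kg).

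**Reverse case.** Seventeen muscles at Z = −1 and one at Z = 0 give a baseline of −17/18 = −0.944. If the strong muscle is missed once and nothing has changed, the visit mean is −1.000: a false decline of 0.056.

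**Frequency.** The documents give no rate of late muscle loss. The muscle-strength row of the Part A schedule is broken in the available text. If testing is on Day 1 and at Weeks 8, 16 and 24, and losses are evenly spread, one third fall after Week 16.

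**The case against.** **The zero rule may already cover the case.** The operative condition is that the value stays missing through the final assessment; two consecutive missing values are only an example. Week 24 appears to be the last muscle-strength assessment, so a programmer could score a single final missing value as zero. That reading is open, though the notion of a value continuing to be missing points the other way. Two programmers could derive different confirmatory results, which is itself a reason to settle the wording. Isolated misses at earlier visits leave the average on either reading.

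**A muscle too weak to test may be recorded as 0 kg.** The documents do not say. If it is, the Week 24 artefact for such muscles disappears. The zero rule suggests that the sponsor expects missing values.

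**A reader might infer that a participant who loses a muscle at Week 24 will appear to gain strength.** The figures do not support that in general. The lost muscle must have been weaker than the others, and the others must fall little: less than about 0.15 Z for two muscles and 0.31 Z for four in the 0.5 SD case. Otherwise the decline is only understated.

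**A reader might also infer that the rule hides a real benefit.** This is not established. If losses after the penultimate visit are commoner in the faster-declining arm, that arm is flattered. But a drug that delays loss from before the penultimate visit to after it moves a participant from the zero rule to the dropped muscle. In the four-muscle example that is −0.189 against +0.207, a spurious 0.396 in the drug's favour. The net direction depends on the timing of losses by arm. No type I error problem is shown either: with no treatment effect, similar missingness would be expected in both arms.

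**A sensitivity analysis may exist in text that is not visible.** The SAP calls this the derivation for its primary analysis, so alternatives may be defined elsewhere. The point concerns the main derivation.

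**Conclusion.** The concern holds in limited form. As written, the change in megascore can compare different sets of muscles, and the model cannot undo that. If a muscle weaker than the rest is first missing at Week 24, the participant's change is too favourable, by 0.09 to 0.36 Z in the scenarios examined, with a reversed sign in some of them. A stronger-than-average muscle missed once has the opposite effect.

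This rests on three conditions: untestable muscles are recorded as missing, a single final missing value is not scored as zero, and the assumed strengths are realistic. The size of the effect on the treatment comparison is unknown and its direction undetermined. The megascore is tested only if the primary endpoint and four secondary endpoints are all significant, and no earlier test in the sequence is affected. It is worth correcting because the correction is cheap, not because the trial's main conclusion is at risk.

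**What to change.** In SAP 3.3.1.1 and Table 2:

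1. Define the change in megascore at each visit as the mean of (Z at visit − Z at baseline) over muscles with a value, observed or imputed by the SAP rule, at both baseline and that visit.
2. State the minimum number of paired muscles needed for a score.
3. State whether a muscle first missing at the final assessment because it is too weak to test is scored as 0 kg.

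The cost is wording and one derivation step, with no new data. Two consequences should be stated. The paired change will not always equal the visit megascore minus the baseline megascore, so the SAP should say which baseline value enters the model as covariate. And pairing alone removes the composition artefact in both directions but leaves a muscle lost only at Week 24 contributing nothing: −0.100 rather than −0.189 in the four-muscle example. Item 3 is needed to settle that.

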3.3.1.2 Main analytical approach

Treatment policy will be used for the analyses of all secondary endpoints in Part A and Part B as stated in [Table 2](#).

CAFS

CAFS at Week 24, Week 76 and Week 104 will be analyzed in the same manner as that used to analyze the primary endpoint in Part B in [Section 3.2.2](#).

Continuous Endpoints

Continuous endpoints include:

Part A

- change from baseline in SVC to Week 24
- change from baseline in muscle strength to Week 24
 - change from baseline in megascore to Week 24
 - change from baseline in grip strength to Week 24
- change from baseline in ALSAQ-5 to Week 24
- change from baseline in serum NfL to Week 24

Part B

- change from baseline in the ALSFRS-R total score to Week 52, Week 76, and Week 104
- change from baseline in SVC to Week 52, Week 76, and Week 104
- change from baseline in ALSAQ-5 to Week 52, Week 76, and Week 104
- change from baseline in serum NfL to Week 52

These continuous endpoints will be analyzed using the same manner as that used to analyze the primary endpoint in Part A in [Section 3.2.2](#), except that baseline ALSFRS-R score will be replaced by the baseline value of the corresponding endpoint. Plots of least squares means (\pm standard error) over time will be provided. Plots of mean (\pm SD) and/or mean change (\pm SD) and/or median over time will also be provided. For NfL data, log transformation will be applied in

the MMRM model. The treatment difference will then be back-transformed to the original scale. The back-transformed LS means stand for geometric mean ratios compared to baseline, and the back-transformed LS means difference stands for ratio of the geometric mean ratios compared to baseline between SAR443820 and placebo. In order to assess the impact of deviation from the normality assumption, a sensitivity analysis using rank analysis of covariance (ANCOVA) with the same covariates as for the MMRM analysis except visit and related interaction terms, will be performed to provide the p-value for the comparison between the treatment groups.

Time-to-event endpoints

Time-to-event endpoints in Part B include:

[figure not shown]
- time from baseline to occurrence of either death or permanent assisted ventilation (>22 hours daily for >7 consecutive days), whichever comes first
- time from baseline to the occurrence of death

For the time-to-event endpoints, baseline is defined as randomization. The time to event will be modeled by a Cox proportional hazards model. The covariates included in the model are treatment group, randomization strata of the geographic region of the study site, ALS onset region (bulbar or other areas), use of riluzole (yes or no), use of edaravone (yes or no), use of the combination of sodium phenylbutyrate and taurursodiol (yes or no), disease duration (from first symptom onset to the screening visit), baseline ALSFRS-R score and baseline NfL. The hazard ratio between SAR443820 and placebo, its 95% confidence interval and the p-value for comparing SAR443820 and placebo will be estimated from this model with robust variance estimation (9). Comparison between SAR443820 and placebo will also be assessed by a log-rank test stratified by randomization strata of the geographic region of the study site, ALS onset region (bulbar or other areas), use of riluzole (yes or no), use of edaravone (yes or no), use of the combination of sodium phenylbutyrate and taurursodiol (yes or no) and baseline NfL (< median baseline NfL or >= median baseline NfL). Kaplan-Meier (KM) plots of the cumulative incidence rate will be provided by treatment group to depict the course of occurrence of event over time. The proportion of participants with events at given time points (eg, Week 4, 8, 12, 16, 20, 24, etc.) and median time to event (if feasible) will be calculated using the KM estimates.

